Laboratory evidence of adrenal insufficiency due to the use of topical corticosteroid treatment has been reported, however, physiologic adrenal suppression is a common occurrence of little clinical significance (25). Pathologic adrenal suppression from topical corticosteroid use is a very rare occurrence; after nearly half a century of world-wide topical steroid use, there is only a few clinical cases describing prolonged corticosteroid-induced pathological adrenal suppression (25). Furthermore, these cases occurred in adults using at least two times the maximum recommended dose of super-potent corticosteroids for as long as 18 months or, in the single case that did not exceed this dosage, involved continuous use for 5 years. It is not considered to be ethically justified to perform adrenal function testing on all patients in the present trial, as the risk of clinical adrenal insufficiency with the use of topical corticosteroids is low and such testing involves an invasive technique. Therefore, adrenal function testing will be undertaken in a subset of randomised subjects with at least moderate psoriasis affecting between 10 and 30% of the BSA. The aim is to achieve approximately 25 subjects undergoing HPA axis testing after 52 weeks of exposure. The testing will be done at selected trial sites using the ACTH stimulation test. The proposed sample size is in line with the typical sample size for trials evaluating effect of topical corticosteroids on the HPA axis function (26) and also a previous recommendation by the US Food and Drug Agency (FDA) for a maximum use systemic exposure trial (LEO 90100-30). Testing will be done at baseline, at the end of the initial open-label phase (Week 4), at Week 28, and at the end of trial (Week 56 or at early withdrawal).

Subjects will need to give a separate written consent for having ACTH challenge tests performed. If they do not agree to the having ACTH challenge tests performed, they may still participate in the main part of the trial.

Local safety and tolerability will be evaluated by the scoring of application site skin reactions using the same assessment as used in the short-term trials with LEO 90100. Clinical signs and symptoms will be assessed on a 4-point scale (from absent to severe). Perilesional erythema, oedema, dryness, and erosion will be assessed by investigator and application site burning or pain will be assessed by subject.

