5.3 Safety assessments

- Adverse events of concern associated with long-term corticosteroid use
- Incidence of rebound (as defined in section [11.3.6.2](#))
- Local safety and tolerability assessment scores
- Effect on calcium metabolism, based on change from baseline in serum calcium and spot urinary calcium at Week 4 and the end of trial
- Effect on HPA axis (in a subset of subjects with disease involvement of between 10 and 30% of BSA), based on serum cortisol ≤ 18 mcg/dL 30 minutes after cosyntropin injection at Week 4, Week 28, and end of trial (Week 56) or early withdrawal.

[figure not shown]
Exposure and standard safety data will be reported as described in sections [11.3.3](#) and [11.3.6](#).

6 Trial Design

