8.12.1 Safety Laboratory Blood Analysis

Blood samples (27.5 ml) for biochemistry must be collected at the time points specified in the schedule of trial procedures (section 8.1).

Because there will be no repeated blood sampling, venepuncture will be used rather than indwelling catheters to minimise subject discomfort and to reduce the extent of invasive procedures.

Collection, handling and shipment instructions for blood samples for biochemistry are provided in a separate laboratory manual.

Biochemistry

The following analysis will be performed on the serum blood samples:

- Calcium – in samples collected at baseline (Visit 1), after 4 weeks (Visit 2) and at the end of trial (Visit 15, or at withdrawal from trial), plus at FU1 Visit if applicable
- Albumin - in samples collected at baseline (Visit 1), after 4 weeks (Visit 2) and at the end of trial (Visit 15, or at withdrawal from trial), plus at FU1 Visit if applicable
- 25-OH vitamin D - at baseline (Visit 1) only

Albumin-corrected serum calcium will be calculated in mmol/L using the formula:

Serum calcium (total) in mmol/L + (0.02 x [40-serum albumin in g/L]).

The (sub)investigator must evaluate all results outside the reference range ('clinically significant' or 'not clinically significant') and sign and date. If any of the laboratory results are abnormal and judged as clinically significant, it should be recorded as an adverse event and the (sub)investigator should follow up with the subject as clinically appropriate.

If the albumin-corrected serum calcium result is above the normal reference range at Visit 2, sampling should be repeated at the next visit. If the albumin-corrected serum calcium result is above the reference range at the last on-treatment visit, a follow-up visit should be performed for repeat sampling.

For subjects undergoing ACTH challenge test (Assigned sites only)

Adrenal function testing will be undertaken in a subset of randomised subjects with psoriasis affecting between 10 and 30% of the BSA. The aim is to include 25 subjects undergoing HPA axis testing after 52 weeks of exposure.

The samples listed above will be taken before the ACTH-challenge test that is also scheduled for these visits.

The t=0 (baseline) measurement of serum cortisol concentration for the ACTH-challenge test will be made from the biochemistry sample.

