The ACTH-challenge test will be performed at baseline (Visit 1), after 4 weeks (Visit 2), after 28 weeks (Visit 8) and at the end of trial (Visit 15 or at early withdrawal). If the subject withdraws prior to completing the initial open-label treatment phase, the ACTH-challenge test scheduled for Visit 2 should not be performed. If the subject discontinues the trial prior to week 56 (this also includes discontinuation due to not achieving 'clear' or 'almost clear' disease status following 4 weeks of once daily treatment following a relapse in psoriasis status), a follow-up visit must be scheduled within 7 days of the last treatment period visit for the purpose of performing the ACTH-challenge test, if the test was not performed on the same day (rescheduling required due to the time dependency of the ACTH-challenge test).

Subjects will not be included in this procedure of the trial if one of the following applies to the serum cortisol concentration at Visit 1:

- ≤ 5 mcg/dl pre-stimulation (before CORTROSYN® / Synacthen® injection)
- ≤ 18 mcg/dl at 30 minutes after CORTROSYN® / Synacthen® injection

If the ACTH challenge test at Visit 15 (end of maintenance phase) or at early withdrawal shows a serum cortisol concentration ≤ 18 mcg/dl at both 30 minutes and 60 minutes after the ACTH challenge, a further ACTH-challenge test is required 4 weeks later (FU2 visit).

If the results of the ACTH-challenge test at the FU2 visit continue to show a serum cortisol concentration ≤ 18 mcg/dl at both 30 minutes and 60 minutes after ACTH challenge, further ACTH challenge tests should be performed, but not more often than at 4-weekly intervals, until the adrenal suppression resolves (i.e. serum cortisol concentration > 18 mcg/dl at 30 minutes or at 60 minutes after the ACTH challenge, or at both time-points). The data from such further ACTH challenge tests must be captured in the unscheduled follow-up visit page in the eCRF.

The following procedures should be performed prior to the ACTH challenge tests: Heart rate and blood pressure, blood/urine sampling for central laboratory analysis (biochemistry/urinalysis), blood sampling for biomarkers and urine pregnancy test (in female subjects of child-bearing potential).

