11.3.8 General Principles

All significance tests will be two-sided using the 5% significance level. All confidence intervals will be presented with 95% degree of confidence.

An observed cases approach will be used for tabulations of data by visit (i.e. involving only those subjects who attended each specific visit).

Categorical data will be summarised using the number and percentage of subjects in each category and treatment group. Continuous data will be summarised using the mean, median, standard deviation (SD), minimum and maximum values.

All the analyses specified in the protocol will be reviewed in relation to the blinded data actually obtained and the statistical analysis plan update will be finalised before breaking the randomisation code.

The randomisation is stratified by treatment group, trial site, HPA axis testing and disease severity at baseline as factors. Usually, the statistical analysis of efficacy parameters takes all the stratification factors into account. However, the HPA axis test is a safety parameter, which is only determined at a small subset of sites and subjects. Hence stratification by HPA axis test is not applicable for all sites. Also, it is expected that two subjects per site will be randomised. This means that a statistical model having HPA axis testing as a factor may not converge, depending on whether subjects participating in the HPA axis test drop out. Furthermore, the inclusion criteria for participating in the HPA axis test are “Moderate” or “Severe” in the baseline PGA assessment and a baseline BSA between 10 and 30%. Including the stratification factor HPA axis testing would therefore introduce a confounding with the

stratification according to baseline PGA as well as sites. Therefore the stratification according to HPA axis testing is not included in the statistical analyses.

Any changes from the statistical analysis planned in this clinical trial protocol will be described and justified in a protocol amendment/the statistical analysis plan update and/or in the clinical trial report dependent on the type of deviation.

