Appendix 4: Definitions of Adverse Events and Serious Adverse Events

Adverse Event Definition

An adverse event is defined as any untoward medical occurrence in a patient or clinical investigation subject administered a pharmaceutical product and which does not necessarily have a causal relationship with this treatment. An adverse event (AE) can therefore be any unfavourable and unintended sign (including an abnormal laboratory finding), symptom, or disease temporally associated with the use of a medicinal (investigational) product, whether or not related to the medicinal (investigational) product. (ICH Harmonized Tripartite Guideline for Good Clinical Practice, E6 (R1)).

This definition includes:

- accidental injuries, events related to trial procedures, reasons for any unfavourable and unplanned change in medication (drug and/or dose), clinically significant worsening of pre-existing conditions, or reasons for admission to hospital or surgical procedures unless these were planned before enrolment. It also includes AEs commonly observed and AEs anticipated based on the pharmacological effect of the investigational product. In addition, any laboratory abnormality assessed as clinically significant by the (sub)investigator must be recorded as an AE.

Serious Adverse Event Definition

A serious adverse event (SAE) is any untoward medical occurrence that

- results in death
- is life-threatening
- requires inpatient hospitalisation or prolongation of existing hospitalisation. Planned hospitalisation or planned prolonged hospitalisation do not fulfill the criteria for being an SAE but should be documented in the subject's medical record.
- results in persistent or significant disability/incapacity
- is a congenital anomaly/birth defect

or

- is a medically important condition. Events that may not be immediately life-threatening or result in death or hospitalisation but may jeopardise the subject or may require intervention to prevent one of the other outcomes listed in the definition above. Examples are intensive treatment in an emergency room or at home for allergic broncospasm, blood dyscrasias and convulsions that do not result in hospitalization, development of drug dependency or drug abuse.

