5.5.7 ACTH-Challenge Test

Open-label phase:

For the group of subjects undergoing the ACTH-challenge test, the number and percentages of subjects with serum-cortisol concentration values ≤ 18 mcg/dl at 30 minutes and 60 minutes after the ACTH-challenge test will be summarised by visit.

The serum-cortisol concentration at time 0 (just before the ACTH-challenge test) and at 30 and 60 minutes after ACTH-challenge at visit 1 and visit 2 will be summarised.

Trial ID: LP0053-1004	Date: 15-JUL-2019	Version: 1.0 Page 35 of 177
-----------------------	-------------------	--------------------------------

Individual data for subjects with serum cortisol concentration values ≤ 18 mcg/dl at either 30 or at 60 minutes after ACTH-challenge in the open-label phase will be tabulated.

A mean plot of the serum-cortisol concentration at time 0, and at 30 and 60 minutes after the ACTH-challenge test for visit 1 and visit 2 will be done.

Maintenance phase:

The number and percentages of subjects with serum-cortisol concentration values ≤ 18 mcg/dl at 30 minutes and 60 minutes after the ACTH-challenge test will be summarised by visit and by treatment group.

The serum-cortisol concentration at time 0 and at 30 and 60 minutes after ACTH-challenge tests will be summarised by visit and treatment group.

Individual data for subjects with serum cortisol concentration values ≤ 18 mcg/dl at either 30 or at 60 minutes after ACTH-challenge will be tabulated.

A mean plot of the serum-cortisol concentration at time 0, and at 30 and 60 minutes after the ACTH-challenge test by treatment group will be done.

Results from ACTH-tests performed at early termination visits will be listed only and are not included in the above-mentioned tables and figures.

More details for the tables and listings can be found in [Appendix I](#) and [Appendix II](#).

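### ACTH tests done at early withdrawal after randomisation appear in a listing only, although the protocol makes them part of the HPA-axis safety measure

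*SAP*

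**What the plan says.** Protocol 5.3 defines the HPA effect by serum cortisol at or below 18 mcg/dl 30 minutes after injection, "at Week 4, Week 28, and end of trial (Week 56) or early withdrawal". Protocol 3.3.3 places the last test "at the end of trial (Week 56 or at early withdrawal".

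Protocol 8.12.1 makes the test mandatory for subjects who discontinue before Week 56. If it is not done on the day, a visit must be "scheduled within 7 days of the last treatment period visit for the purpose of performing the ACTH-challenge test". The section expressly includes subjects who leave because they did not regain clear or almost clear "disease status following 4 weeks of once daily treatment following a relapse in psoriasis status". Protocol 11.3.6.4 asks for the count at or below 18 mcg/dl over time by treatment group and leaves out no early-withdrawal test.

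SAP 5.5.7 describes the maintenance-phase tables and figure and closes with: "Results from ACTH-tests performed at early termination visits will be listed only and are not included in the above-mentioned tables and figures". Shells 97 and 98 and Figure 3-2 carry Visits 2, 8 and 15 only.

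**The concern.** The protocol counts an early-withdrawal test as an end-of-treatment result. The SAP removes it from the cortisol summary (Table 3-88), the individual data for subjects at or below 18 mcg/dl (Table 3-89), the counts (Table 3-90) and Figure 3-2. What remains is the ACTH listing (Listing 8-7).

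The Visit 15 rate then describes only those who stayed. Failure of rescue treatment forces withdrawal, so those who stayed are a selected group. SAP 5.7 makes this same argument when it drops by-visit summaries of m-PASI, BSA, DLQI and other measures. For early leavers the tables give no count, denominator or comparison by arm. Long-term safety is a secondary objective, and protocol 3.3.3 names possible systemic effects of prolonged or repeated use as a main question.

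The direction of any bias cannot be inferred. Early leavers may have had recent daily rescue treatment, but they also have shorter exposure and may be tested some days after stopping.

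**Working it through.** **1. What the tables still show for someone who leaves early**

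| Result | Where it is reported |
|---|---|
| Visit 2 test, subject leaves at the end of the open-label phase | Tables 3-85 to 3-87 |
| Visit 2 test, randomised subject | Tabulated, but taken before any maintenance treatment |
| Visit 8 test, if reached | Tabulated |
| Early-withdrawal test after randomisation | Listing only |
| FU2 retest, about 4 weeks later | Table 3-91, but FU2 is triggered only by values at or below 18 mcg/dl at both 30 and 60 minutes |
| Value judged clinically significant | Adverse event: "abnormal and judged as clinically significant, it should be recorded as an adverse event" (protocol 8.12.1), and "any laboratory abnormality assessed as clinically significant by the (sub)investigator must be recorded as an AE" (protocol Appendix 4) |

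A result that is low at 30 minutes only, which meets the protocol 5.3 criterion, and is not judged clinically significant is in no table. A randomised subject who leaves before Visit 8 has no post-randomisation ACTH result in any table unless FU2 is triggered.

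**2. Inputs for the size**

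- Target: about 25 subjects tested after 52 weeks of exposure (protocol 11.1).
- Drop-out: 30% over 52 weeks with exponential decline (protocol 11.1). This is the overall trial figure. Its use for the HPA subset is an assumption, so 20% and 40% are also shown.
- Every drop-out is tested (assumption, relaxed in step 4).

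**3. The protocol's own figure**

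Still in the trial at week t after randomisation = 380 × 0.7^(t/52).

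- t = 22: 326.8 (stated 326).
- t = 48: 273.4 (stated 273).

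The drop-out model is reproduced.

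**4. Listing-only tests**

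Randomised to the HPA part: N = 25/(1 − d), rounded up. Listing-only tests = N − 25. Share leaving before Visit 8 (24 weeks after randomisation) = 1 − (1 − d)^(24/52).

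| Drop-out d | N | Listing-only | Share of end-of-treatment tests | Leaving before Visit 8 |
|---|---|---|---|---|
| 20% | 32 | 7 | 21.9% | 32 × (1 − 0.9021) = 3.1 |
| 30% | 36 | 11 | 30.6% | 36 × (1 − 0.8482) = 5.5 |
| 40% | 42 | 17 | 40.5% | 42 × (1 − 0.7900) = 8.8 |

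About half of expected drop-outs (N × d) leave before Visit 8: 49%, 51% and 53%. For them the listing-only test is the only scheduled ACTH test after randomisation.

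If only half of the drop-outs are tested at d = 30%, about 11/2 = 5.5 tests are affected, or 5.5/30.5 = 18%.

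**5. Per arm**

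With 1:1 allocation and 30% drop-out, each arm has about 25/2 = 12.5 tests at Visit 15 and 11/2 = 5.5 listing-only tests. With no suppression seen at Visit 15, the exact 95% upper limit is 1 − 0.025^(1/n): 26.5% for 0/12 and 24.7% for 0/13. At this size a few additional results change what the table conveys.

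**The case against.** - **Nothing is lost.** Every early-withdrawal result is listed, and about 11 rows, or 5 to 6, can be counted by hand. This is true. But the reader has to build the count, denominator and arm comparison for a measure that the protocol itself names.
- **FU2 recovers part of the count.** FU2 follows suppression at both time points, whether found at Visit 15 or at early withdrawal, and Shell 100 prints the number at FU2 by arm. Subtracting the Visit 15 row of Table 3-90 would give the early leavers. This works only if every triggered subject attends, and it misses low values at 30 minutes only.
- **The remaining gap is narrow.** Protocol 6.1.5 and 8.12.1 regard suppression as resolved if either time point exceeds 18 mcg/dl. Even so, protocol 5.3 and 11.3.6.4 keep the 30-minute criterion for the analysis.
- **The rule has a basis.** By-visit tables use observed cases, "involving only those subjects who attended each specific visit" (protocol 11.3.8), and the subset was sized for 52-week exposure. That justifies keeping these tests out of the Visit 15 row. It does not rule out a separate row, and it does not explain their exclusion from Table 3-89, which is individual data; Shell 99 has a generic visit column that can already hold them.
- **A small mixed row says little.** SAP 5.5.8 and 5.5.9 tabulate early discontinuers within a much larger safety set (Table 8 of the SAP totals 545 randomised). The row proposed here would be small and would mix exposure times. That is a reason for clear labelling.
- **The 31% is a ceiling at 30% drop-out.** It needs every leaver to be tested, and some will not return for an 08:00 test. This stands, and the half-tested case is the response to it. The confidence limits reflect the small subset, not the listing rule.

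**Conclusion.** The concern holds. The protocol makes the early-withdrawal ACTH test part of the HPA measure and requires it to be done, while the SAP leaves it out of every table and figure for randomised subjects. The SAP gives no reason and has no entry in 5.7, although protocol 11.3.8 asks that changes from the planned analysis be described and justified.

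Under the stated assumptions about 31% of end-of-treatment tests are affected at 30% drop-out (22% at 20%, 40% at 40%), falling to about 18% if half of the leavers are tested at 30%. The true share in the HPA subset is not given in the documents. This is a gap in how a named safety measure is reported. It changes no hypothesis test or efficacy endpoint, and no direction of bias is claimed. It should be fixed because the correction is small.

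**What to change.** Replace the closing sentence on early-termination tests in SAP 5.5.7 with a rule on these lines:

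- The Visit 15 row and Figure 3-2 are unchanged.
- ACTH tests at early withdrawal after randomisation are summarised by treatment group in a separate row, labelled *Early withdrawal*, in Tables 3-88 and 3-90. The row also reports time since randomisation, days since last IMP application, and the number of subjects who used rescue IMP in the 28 days before the test.
- Subjects at or below 18 mcg/dl at 30 or 60 minutes at early withdrawal are included in Table 3-89.
- Any combined row is labelled as the end-of-treatment test at Visit 15 or early withdrawal, and supplements the Visit 15 row.

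The cost is one SAP sentence, one extra row in Tables 3-88 and 3-90 (Shells 97 and 98), extra entries in Table 3-89 and three simple derivations. The protocol already requires the tests, and the End of Trial Form (protocol 8.19) records the date of last dose. Where the last application date is missing, SAP 5.5.1 substitutes the last visit attended, so days since last application may be imputed for some subjects. The early-withdrawal row mixes exposure durations, and some tests may fall up to 7 days after the last treatment visit. The Visit 15 row remains the 52-week result.

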5.5.8 Vital Signs and Physical Findings

Open-label phase:

The change in vital signs (blood pressure, heart rate) from baseline to end of open-label treatment phase will be summarised.

Maintenance phase:

The change in vital signs (blood pressure, heart rate) from randomisation to end of trial will be summarised.

In addition, the change in vital signs from randomisation to end of maintenance phase for subjects discontinuing before 6 months after randomisation, the change in vital signs from randomisation to end maintenance phase for subjects discontinuing on or after 6 months after

Trial ID: LP0053-1004	Date: 15-JUL-2019	Version: 1.0 Page 36 of 177
-----------------------	-------------------	--------------------------------

randomisation, and the change in vital signs from randomisation to visit 15 will be summarised.

If more than one vital sign value is reported for the same visit and time point, the latest value will be used in summary statistics and analyses.

If vital sign measurements are missing for a subject at baseline or at randomisation the change from baseline or randomisation to a specific visit will not be calculated.

Further details for the tables can be found in [Appendix I](#) and [Appendix II](#).

Findings from physical examinations and vital signs data will be listed. More details can be found in [Appendix I](#).

